# Abbreviations

AUD Alcohol Use Disorder

AUDIT Alcohol use disorder identification test

CBT Cognitive behavioral therapy

DAT Dopamine Transporter

DSM-5 Diagnostic and Statistical Manual of Mental Disorders

fMRI Functional magnetic resonance imaging (brain-scan)

FSL FMRIB Software Library - Analysis tools for FMRI

GLP1-RA Glucagon-like peptide-1 receptor agonists

Heavy drinking day Alcohol consumption over 60/48 g (men/women) of alcohol per day

ICD-10 International Classification of Diseases

PEth Phosphatidylethanol - Biomarker for alcohol consumption

REDCap Web application for building and managing online surveys and databases

SPECT Single-Photon Emission Computed Tomography (brain scan)

SPM Statistical Parametric Mapping (software for analysis of fMRI data)

TLFB Time-Line-Follow-Back Method (recording of heavy drinking days)

Edition: 1.0

EudraCT 2016-003343-11

# Introduction

## Background and rationale

Alcohol use disorder (AUD) is a major public health problem both in Europe and in the United States. AUD is under-diagnosed and undertreated and when alcohol abstinent, more than 2/3 of patients in abstinence - oriented treatment will relapse within the first year. In Denmark, approximately 20% of the population is consuming more alcohol per week than recommended by the Danish Health and Medicines Authority, 14% of the Danish population has a harmful consumption of alcohol and 3% fulfills the criteria for AUD. One of the best-documented modalities in the treatment of AUD is cognitive-behavioral therapy (CBT). The underlying neuroanatomical basis of alcohol addiction and treatment effects of CBT are not yet established though functional Magnetic Resonance Imaging (fMRI) studies have begun to elucidate the neuroanatomical basis.

The pharmacological treatment of AUD is considered an important supplement to psychological therapy. Disulfiram, a substance that blocks alcohol-metabolizing enzymes resulting in increased acetaldehyde concentrations, has been introduced in Denmark many years ago and is still the most used drug against AUD in Denmark. Newer pharmacological agents as acamprosate and naltrexone have been introduced to the clinic. However, these compounds have not, despite numerous randomised clinical trials (RCT), gained widespread dissemination, probably because the effect of these substances has been modest, with a less than 10% increase in abstinent rate compared to placebo.

As the success rates of CBT are moderate and the synergistic effects of adding pharmacological treatment – as described above – are quite limited, strong needs still exist for efficient, molecular targets in the medical treatment of alcohol dependence.

GLP-1 based therapy was introduced to the market for the treatment of type 2 diabetes in 2006. GLP-1 is an incretin hormone, which is secreted from endocrine L cells of the small intestine in response to nutrients in the gut lumen. Exendin-4, originally isolated from the saliva of a lizard species, the Gila monster, has 53% sequence homology with human GLP-1 in its first 30 amino acids. Synthetic exendin-4, referred to as exenatide, is resistant to DPP-4 cleavage and therefore has a significantly longer half-life which makes it useful for the treatment of type 2 diabetes.

GLP-1RA has a well-established effect on food reward which seems to be driven by two key mesolimbic brain structures, the ventral tegmental area (VTA) and nucleus accumbens (NAc). These structures are not only involved in the rewarding properties of food but also drugs of abuse, including alcohol. A link between alcohol intake and GLP-1 has been demonstrated in studies, as alcohol intake can result in an elevated level of gut-produced GLP-1 in rats. Elevation of dopamine levels in brain striatum following stimulant administration has been demonstrated in multiple clinical trials and dopamine is considered to have a central role in addiction to stimulant drugs (i.e. amphetamine, alcohol). Preclinical studies have demonstrated the inhibitory effects of the GLP-1RA exendin-4 on alcohol-mediated behavior in rodents and

Edition: 1.0

EudraCT 2016-003343-11

non-human primates. The precise mechanism of action has not been elucidated; however, we have recently reported that exendin-4 induced upregulation of the dopamine transporter (DAT) function in vitro.

GLP-1 analogs: A potential new treatment for alcohol use disorder?

Based on the identified medical need for novel molecular targets in the medical treatment of AUD and the promising data of GLP-1R stimulation in alcohol-mediated behavior in rodents, non-human primates and patients with type 2 diabetes, we aim to investigate whether these beneficial findings on alcohol consumption can be extended to encompass patients with known alcohol use disorder.

# Objectives

- Treatment with exenatide will decrease alcohol consumption, measured as the total number of heavy drinking days, for the last 30 days, measured by the Time-Line-Follow-Back-Method, in patients with alcohol use disorder.
- Exenatide will induce upregulation of the striatal DAT availability, in patients with alcohol use disorder quantified by SPECT-scans.
- Exenatide will modulate neural responses in reward processing brain regions including NAc quantified by fMRI-scans.

# Study Methods

#### Trial design

The EXALT trial¹ was a randomised, double-blinded, place bo-controlled clinical trial for 26 weeks and a long term follow up 26 weeks after the end of participation in the main trial. Comparative treatment regimens were once-weekly injections with exenatide 2 mg (Bydureon®) or placebo (saline) as a supplement to cognitive behavioral therapy. Baseline data were collected at the screening session. Follow-up meetings were scheduled at weeks 4, 12, 20, and a final evaluation at week 26.

A subgroup of patients had a baseline SPECT- and an fMRI scan or just an fMRI scan performed before receiving 1. injection, and again when they finalized the study.

A group of 25 individuals matched with age, gender, education, and no history of alcohol use disorder had the same screening blood-samples and the same fMRI scan performed.

#### Randomization

The participants were randomised in two groups, exanetide or placebo. The randomisation was stratified in terms of age, sex, and baseline alcohol consumption i.e. the number of heavy drinking days in the last 30 days before inclusion measured by the TLFB-method (5-11, 12-17, 18-23, 24-30 days). For this stratified randomisation, the randomisation tool in REDCap was used. Patients, investigators, other caregivers performing assessments, and persons performing data analysis have been blinded from the time of randomisation and until the time of database unlock. To maintain the blinding, the participants were blindfolded and an un-blinded nurse prepared the injections in a separate room and gave the injection immediately after.

## Sample size

The original sample size calculation was performed with an estimated drop-out rate of 40 % and a power of 90%. That led to a total number of 114 patients to include. Please see appendix 1. In May 2019 when recruitment was almost finished, the dropout rate was nearly 60%. We choose as a consequence to do a

# Psychiatric Centre Copenhagen, Rigshospitalet

26.05.20

Statistical Analysis Plan

Edition: 1.0

EudraCT 2016-003343-11

new power calculation with a drop out rate of 60% and a power of 85% (please see below). Due to a lack of patients to be included we stopped recruitment 1st of October 2019.

#### Justification of sample size incl. power calculation

The primary outcome measure, i.e. the total number of heavy drinking days, was used for the sample size calculation. Based on data from the study by Johnson et al, where the reduction in the percentage points of the total number of heavy drinking days was 60 pp in the intervention group and 33 pp in the control group. With an alpha of 5%, and a power of 85%, and with an estimated SD of 34.5, the estimated sample size was of 58 patients (29 in each group). With an estimated dropout rate of 60% a total number of 144 patients (72 patients in each arm) was needed (please see below)

#### Heavy drinking days:

Reduction in heavy drinking days: Topiramate versus placebo: 60.34 contra 32.73

SD estimate 34.5

#### The POWER Procedure

Two-sample t Test for Mean Difference

Fixed Scenario Elements

Distribution	Normal
Method	Exact
Group 1 Mean	60.34
Group 2 Mean	32.73
Standard Deviation	34.5
Number of Sides	2
Null Difference	0
Alpha	0.05

# Computed N per group

Nominal	Actual	N	Per
Index	Power	Power	Group
1	0.85	0.85	29

## Framework, Statistical interim analysis and stopping guidance

No superiority, equivalence, or noninferiority hypothesis testing framework will be performed. No interim analysis was performed.

### Timing of final analysis

All analyses will be carried out with the treatment groups still blinded and labeled as "treatment group A" and "treatment group B". Before dividing participants into group A and group B, the statistical analysis plan will be completed, signed, and uploaded at clinicaltrials.gov, and the data set locked. The final unblinding of treatment groups (exanetide or place bo), will not be carried out until all statistical analyses are performed.

**EXALT study** 

Statistical Analysis Plan

Edition: 1.0

EudraCT 2016-003343-11

All data besides data from the long term follow up, will be analysed collectively. The last long-term follow up-visit is in September 2020, and the final data will be analysed unblinded

# Timing of outcome assessments

All visits are planned from the date of the first injection and are performed + one week (i.e. week 5, 13, 21, 27). All irregularities are recorded as protocol deviations and visit "windows" are within 2 weeks (+/-).

# Statistical Principles

# Confidence and P-values

The level of statistical significance will be with an alpha set at 0.05, two-sided testing, and a confidence interval of 95%. There will be no adjustment for multiplicity.

#### Adherence and protocol deviations

Adherence to the intervention was defined by no more than 3 missed consecutive injections, or 5 missed injections in total during the 26-week period. The un-blinded project nurses kept an individual injection schedule per patient and thereby kept track of the extent of exposure. Adherence to the intervention will be presented as a table of distribution of percentage of weeks with study medication injections in the main treatment period. Protocol deviations will be presented in a table divided into the categories: study procedure, eligibility, and randomisation. Only protocol deviations regarding "lost to follow up" and "withdrawal" will be summarized in the section named this.

# Analysis populations

All analyses will be performed using the intention-to-treat principle on subjects, who were randomized and received at least one dose of the trial compound (Bydureon® or placebo).

# **Trial Population**

# Screening data

Screening data will be presented in the CONSORT flowchart

#### Eligibility

Individuals aged 18-70 diagnosed with AUD according to ICD 10 and DSM-5 with an AUDIT score >15 and with at least 5 heavy drinking days in the past 30 days. Furthermore, no severe psychiatric-, neurological- or somatic disease, history of alcohol withdrawal seizures, diabetes, other substance use disorder, or concomitant pharmacotherapy against alcohol use disorder.

Besides the patients described above, 25 healthy controls matched with sex, age, and education and with no record of AUD were recruited to perform the same fMRI-scans as the patients included in the study.

#### Recruitment

Recruitment began on the 1st of August 2017 an ended 1st of October 2019. The last patient visit in the main study was planned to be the 8th of April 2020, but because of the COVID-19 outbreak, all patients were terminated 14th of March 2020. The final long-term follow up, will take place in September 2020. All participants were recruited from the suburbs of Copenhagen, Denmark.

Statistical Analysis Plan

Edition: 1.0

EudraCT 2016-003343-11

# Withdrawal/Follow up

All patients who have withdrawn from the intervention and have been included for at least eight weeks (steady-state plasma level) were encouraged to participate in the last week 26 follow-up including brain scans at the time of withdrawal. If successful, individuals will be contacted for a long-term follow-up after further 26 weeks. All other individuals e.g individuals who withdraw before eight weeks and lost to follow-up will not be contacted for a long-term follow-up. Data will be presented in a Kaplan Meyer survival curve

#### Baseline Patient characteristics

List of baseline characteristics to be summarised:

- Sex
- Age mean
- Age group (+/- 40 years)
- Education (lower secondary school, upper secondary school, vocational education + short-cycle higher education, medium cycle higher education + higher education)
- Marital status (yes, no)
- Job-status (yes, no)
- Heavy days, mean
- Heavy days group (5-11, 12-17, 18-23, 24-30)
- Baseline AUDIT score, mean
- Baseline AUDIT group (15-19, 20-40)
- 0-days during the prior 30 days to inclusion, mean
- Total alcohol consumption during the prior 30 days to inclusion, mean
- ICD-10 number of diagnostic items (4,5,6)
- DSM-5 group (mild(2-3), moderate(4-5), severe(>6))

Baseline characteristics will be descriptively summarized in a table assessed by the intervention

# Analysis

#### Outcome definitions

#### Primary endpoint

Percentage of heavy drinking days during the last 30 days, at follow-up after 26 weeks of treatment adjusted for baseline (percentage points (pp)). A heavy-drinking day is defined as a day with an excess intake of 60/48 grams (men/women) of alcohol per day. Data will be registered via the Timeline-Follow-Back-method (TLFB).

# Secondary endpoints

- 1. Total alcohol consumption (gram/day) during the last 30 days, at follow up after 26 weeks of treatment adjusted for baseline. Data will be registered via the Timeline-Follow-Back-method (TLFB).
- 2. Percentage of days without any alcohol consumption during the last 30 days, at follow-up after 26 weeks of treatment adjusted for baseline (percentage points (pp)). Data will be registered via the Timeline-Follow-Back-method (TLFB).
- 3. Phosphatidylethanol (PEth) (ng/mL) at follow-up after 26 weeks of treatment, adjusted for baseline.
- 4. Penn Alcohol Craving Scale (PACS) score at follow-up after 26 weeks of treatment, adjusted for baseline.

Rigshospitalet

Statistical Analysis Plan

Edition: 1.0

EudraCT 2016-003343-11

- 5. Alcohol Use Disorders Identification Test (AUDIT) score at follow-up after 26 weeks of treatment, adjusted for baseline.
- 6. Screen for Cognitive Impairment in Psychiatry test (SCIP) score at follow-upafter 26 weeks of treatment, adjusted for baseline and week 4.
- 7. The liver parameter alanine aminotransferase (ALAT) (U/L) at follow up after 26 weeks of treatment, adjusted for baseline.
- 8. The liver parameter gamma-glutamyl transferase (GGT) (U/L) at follow up after 26 weeks of treatment, adjusted for baseline.
- 9. Mean cell volume (MCV) (fL) at follow up after 26 weeks of treatment, adjusted for baseline.
- 10. Short-Form Health Survey (SF-36) score at follow-up after 26 weeks of treatment, adjusted for baseline.
- 11. Symptom Checklist (SCL-92) score at follow-up after 26 weeks of treatment, adjusted for baseline.
- 12. Bodyweight (kg) at follow-up after 26 weeks of treatment, adjusted for baseline.
- 13. Blood pressure (mmHg) at follow-up after 26 weeks of treatment, adjusted for baseline.
- 14. Pulse (PR) at follow-up after 26 weeks of treatment, adjusted for baseline.
- 15. Waist circumference (cm) at follow-up after 26 weeks of treatment, adjusted for baseline.
- 16. Glycemic control parameters HbA1c (mmol/L) at follow-up after 26 weeks of treatment, adjusted for baseline.
- 17. Kidney function (urine albumin/creatinine ratio) at follow-up after 26 weeks of treatment, adjusted for baseline.
- 18. Drug Use Disorders Identification Test (DUDIT) score at follow-up after 26 weeks of treatment, adjusted for baseline.
- 19. Percentage of heavy drinking days during the last 30 days, at the long term follow up 26 weeks after termination of intervention, adjusted for baseline and end of treatment (week 26) (percentage points (pp)).

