### Analysis methods

All continuous outcomes, i.e., change in metabolic parameters, weight, body composition parameters, alcohol use, etc. will be analyzed using ANOVA from baseline to last observation endpoint. Categorical outcomes will be analyzed using chi-square analyses. As the study was conducted as a randomized trial, no covariates adjustment is in principle necessary to assess causal effects.

Edition: 1.0

26.05.20

Statistical Analysis Plan

EudraCT 2016-003343-11

We will use residual plots and qq-plots in combination with Wally plots to validate the normality assumptions of the residuals in the ANOVA models. If the distributional assumption about normality of the residuals does not hold then we will first see if a log-transform of the outcome will result in a model fit that does not appear to violate the assumptions of normality. If the log-transform still does not hold, our next step will be to consider if the lack of fit is caused by inflation, e.g. due to too many observations being zero. Should that be the case we will replace the standard ANOVA model with a zero-inflated gaussian mixture model for the analyses. Should none of these approaches work we will use quantile regression and model the median outcome instead.

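### Secondary endpoint 19 adjusts long-term heavy drinking for week-26 heavy drinking, which is the primary endpoint, so as worded it does not define the long-term effect of assignment

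*SAP*

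**What the plan says.** The SAP's list of secondary endpoints gives, as number 19, the share of heavy drinking days at the long-term visit, "26 weeks after termination of intervention, adjusted for baseline and end of treatment (week 26", in percentage points.

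The same variable at week 26 is the primary endpoint, defined "at follow-up after 26 weeks of treatment adjusted for baseline (percentage points (pp", with no other adjustment term. The first objective states the expected direction: "Treatment with exenatide will decrease alcohol consumption, measured as the total number of heavy drinking days".

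Three other places bear on the reading:

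- Analysis populations: "All analyses will be performed using the intention-to-treat principle on subjects, who were randomized" and received at least one dose.
- Analysis methods: continuous outcomes "will be analyzed using ANOVA from baseline to last observation endpoint", with the remark that a randomised trial does not in principle need covariates to assess causal effects.
- Posthoc analysis: the other six-month follow-up data listed are craving (PACS), PEth, AUDIT and nicotine dependence. Heavy drinking days are not among them.

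**The concern.** The week-26 value is measured after randomisation, at the end of treatment, and the trial's main hypothesis is that treatment changes it. It is not a baseline covariate. Long-term heavy drinking given week-26 heavy drinking answers a different question from whether patients assigned to exenatide drink less heavily half a year after treatment ends.

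Endpoint 19 is the only place where the SAP analyses long-term heavy drinking days. If it is run as a model with both terms, the SAP yields no estimate of the lasting effect of assignment on that outcome. To the extent that the drug works at week 26, a lasting benefit would be understated, and a benefit that had faded could look like an advantage for placebo.

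The section on timing of the final analysis says that the long-term data, with a last visit in September 2020, will be analysed unblinded. The contrast should therefore be fixed beforehand.

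**Working it through.** **1. The SAP's own figure.** The sample-size inputs are "Reduction in heavy drinking days: Topiramate versus placebo: 60.34 contra 32.73", SD 34.5, two-sided alpha 0.05 and power 85%. The difference is 60.34 − 32.73 = 27.61 pp. The exact two-sample t calculation gives 29.03 per group, and power at 29 per group is 0.850. This agrees with "the estimated sample size was of 58 patients (29 in each group". The figure concerns the primary endpoint and is not in question. It is used here only as a source for a week-26 difference.

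**2. What each reading estimates.** Let d26 and d52 be the true benefits of exenatide (pp fewer heavy drinking days) at week 26 and at the long-term visit.

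- *Baseline only:* estimates d52.
- *Baseline and week 26 as covariates:* in a linear model, estimates d52 − b × d26. Here b is the partial slope of long-term on week-26 drinking given baseline. With equal variances, b = (r12 − r01 × r02)/(1 − r01²), where 0, 1 and 2 index baseline, week 26 and long-term follow-up.
- *Change from week 26:* estimates d52 − d26, which is the case b = 1.

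**3. Choice of correlation (assumption).** The SAP gives no between-visit correlation. Its SD of 34.5 accompanies reductions, so it reads as the SD of a change. With a common per-visit SD of 34.5, the SD of a change is 34.5 × √(2(1 − r)). That is 40.8 at r = 0.3, 34.5 at r = 0.5 and 26.7 at r = 0.7. Only r = 0.5 returns the SAP's figure, so it is used here.

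- Equal correlation at all visits: b = (0.5 − 0.25)/(1 − 0.25) = 0.33.
- Correlation decaying with distance (0.5 between adjacent visits, 0.25 between baseline and long-term): b = (0.5 − 0.125)/(1 − 0.25) = 0.50.

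**4. Results, covariate reading, d26 = 27.61.** The shift is 0.33 × 27.61 = 9.2 pp to 0.50 × 27.61 = 13.8 pp.

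| True long-term benefit | Estimate, b = 0.33 | Estimate, b = 0.50 |
|---|---|---|
| 27.6 pp (fully maintained) | 18.4 | 13.8 |
| 13.8 pp (half maintained) | 4.6 | 0.0 |
| 0 (fully faded) | −9.2 (favours placebo) | −13.8 (favours placebo) |

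The identity was checked with 400,000 simulated patients, with correlation 0.3 between baseline and each later visit and 0.5 between the later visits. For a maintained benefit the formula gives 15.2 pp and the simulation 15.3 pp. Adjusting for baseline only returned 27.7 pp.

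**5. Dependence on the inputs.** The shift is proportional to d26. Half the planning difference (13.8 pp) gives 0.33 × 13.8 = 4.6 to 0.50 × 13.8 = 6.9 pp, and d26 = 0 gives none. Letting r run from 0.3 to 0.7 widens b to 0.23–0.70 and the shift to 6.4–19.3 pp, but the ends of that range do not agree with the SAP's SD.

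**6. Change-from-week-26 reading.** A fully maintained benefit gives 27.6 − 27.6 = 0. That is the right answer to whether the arms diverge after treatment stops. It does not measure the long-term effect of assignment.

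**The case against.** The strongest reply is that the covariate reading may not be what was meant. Analysis methods describes ANOVA from baseline and plays down covariates, and the sample size is built on reductions in percentage points. The SAP also uses the word adjusted loosely: the SPECT endpoint is described both as running from baseline and as adjusted for baseline. Endpoint 19 could therefore mean two contrasts, one against baseline and one against week 26, and the first would then already be the wanted analysis. Relapse after stopping is also a legitimate question for an off-treatment visit, and its rationale may stand in the protocol.

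Much of this stands. A reader might infer that every reading breaks the randomised comparison and so conflicts with the intention-to-treat principle. The SAP does not support that. Change from week 26 is itself a post-randomisation outcome, and comparing it between the arms as randomised is valid. Only conditioning on week 26 as a covariate loses the protection of randomisation.

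What does not stand is that nothing needs changing. A reader of endpoint 19 cannot tell which of three analyses will be run, and on two of them the long-term effect of assignment is not estimated. If two contrasts were meant, naming the baseline contrast as the endpoint loses nothing.

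**Conclusion.** The point holds. As worded, endpoint 19 does not define the long-term effect of assignment on heavy drinking days. Read as covariate adjustment, it conditions on a hypothesised result of treatment. Read as change from week 26, it validly answers another question. The SAP contains no other baseline-only long-term analysis of this outcome.

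The illustrated shift of 9.2 to 13.8 pp applies to the covariate reading only. It rests on a week-26 difference taken from a topiramate study, an assumed correlation of 0.5, equal SDs at each visit and a linear model. The direction needs only a benefit at week 26 and a positive partial slope.

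A reader might go on to infer a loss of power, or a given rate of significant results favouring placebo. The SAP does not support such figures: 29 per group is the target for the primary endpoint, and no long-term sample size is given. Nor does the point reach the primary endpoint, which is adjusted for baseline only. It concerns one secondary endpoint and should be corrected before the long-term data are analysed.

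**What to change.** In secondary endpoint 19, delete the reference to the end-of-treatment value, so that the endpoint is adjusted for baseline only, as the primary endpoint is. If maintenance after stopping is of interest, add change from week 26 to the long-term visit as a separate supplementary analysis, labelled with the question it answers.

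The cost is SAP wording; no new data are needed. Precision changes little. At r = 0.5, with 29 per arm used only as a common scale, the standard error with baseline only, against baseline plus week 26, is 7.85 v 8.15 under equal correlation (about 4% smaller). Under decaying correlation it is 8.77 v 8.64 (about 1.5% larger).

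The change does not address selection into the long-term visit. Under Withdrawal/Follow up, "individuals who withdraw before eight weeks and lost to follow-up will not be contacted for a long-term follow-up", so the limits of that comparison should still be stated when it is reported.
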